# **Randomization and Blinding**

All patients meeting the eligibility criteria for this study will be enrolled. Cluster randomization will be used for this study given impracticability of patient-level 1:1 parallel randomization (see Informed Consent section for details). The EMN and SSCB platforms will be

randomly allocated to our two operating rooms each day. All patients undergoing a navigational bronchoscopy will have their procedure performed with the platform assigned to their operating room (OR) for the day. A biostatistician not involved in patient care will generate the randomization sequence. Random permuted blocks may be used to ensure balanced cluster allocation. A bronchoscopy scheduler with no knowledge of the allocation scheme will schedule each patient into one of the two operating rooms. Allocations will be concealed in sealed envelopes which will be opened every morning by the OR staff preparing the rooms.

It is not possible to blind the bronchoscopist or the patient to the platform used for each procedure, as they are both large distinctive-appearing pieces of equipment. However, thoracic pathologists and bronchoscopy schedulers will remain blinded, such that allocations should be unable to influence their histopathological interpretation or scheduling of procedures in a given OR, respectively.

#### **Study Procedures**

Written research informed consent for the collection of data will be integrated within the clinical workflow when obtaining procedural consent (refer to Informed Consent section below) and all eligible patients will be enrolled. An allocation envelope will be opened by OR staff each morning to determine which room each platform will be set up in. The pre-operative steps and procedure will proceed per usual standard of care. Intubation and ventilation will follow our standard clinical protocol which is identical for both platforms (8.5 mm size endotracheal tube, a recruitment maneuver once the endotracheal tube is secured (PEEP of 40 cmH20 for 40 seconds), followed by ventilation with a PEEP of 15 cmH20 with as minimal FiO2 needed to maintain a SpO2 of >90%). The navigation procedures will be planned using pre-procedure CT scans of the chest and the planning software specific to each platform.

Bronchoscopy will be performed by interventional pulmonologists with expertise in navigational bronchoscopy and as per standard of care. Procedures will be performed under general anesthesia with neuromuscular blockade. Radial endobronchial ultrasound will be available for all procedures. Biopsies will be obtained using transbronchial needles, biopsy forceps, cytology brushes, cryoprobes, and/or other sampling devices at the discretion of the

bronchoscopist. Rapid on-site evaluation will be performed to assess for specimen adequacy. Additional biopsies obtained without the use of guided bronchoscopy (e.g., sampling of central lymph nodes using the linear endobronchial ultrasound bronchoscope) will be collected if clinically indicated but will be excluded from PPL diagnostic yield calculations. The procedure will be deemed non-diagnostic if the proceduralist is unable to reach the nodule (no biopsies obtained, representing navigation failure) or if a complication occurs before biopsies are obtained. All patients will recover based on our usual standard of care, which includes two hours of monitoring in the PACU before being discharged.

Patients not diagnosed with malignancy following bronchoscopic biopsy will be followed clinically per standard of care. We will review their interval chest CT scans to assess the target lesion for progression, regression, or stability for up to 12 months. If any additional biopsies of the target lesion are obtained by alternative means (transthoracic needle biopsy, surgical biopsy), definitive pathological results as previously defined will be compared to the bronchoscopy biopsies.

Study Procedures	Day 1	Within 7 Days	3 Month	6 Months	12 Months
Inclusion/exclusion criteria	X				
Randomization	Х				
Clinical and demographic data	Х				
Adverse events	Х	Х			
Pathology review		Х			
Chest CT	Per SOC		Per SOC	Per SOC	Per SOC
Bronchoscopy	Per SOC				
Follow-up			Per SOC	Per SOC	Per SOC

## **Study Calendar**

# Assessment of Resource(s)

The Interventional Pulmonology group at Vanderbilt University Medical Center performs approximately 400 navigational bronchoscopies per year and is one of the leading centers in navigational bronchoscopy in the US, both from a volume and expertise standpoint. The group generally consists of three full time board-certified interventional pulmonologists, an interventional pulmonology fellow, a dedicated interventional pulmonology nurse practitioner, and a dedicated group of outpatient personnel (nurses, nurse navigators, and dedicated schedulers). Obtained samples are analyzed per standard of care by a group of thoracic pathologists. Anesthesia for the procedures will be provided by general and cardiothoracic anesthesiologists supervising CRNAs with specific expertise in bronchoscopy anesthesia.

## **RECRUITMENT AND ENROLLMENT PROCEDURES**

The vast majority of navigational bronchoscopy procedures at VUMC meet eligibility criteria for this study, with very few procedures annually being performed in pediatric patients or for alternative studies requiring a specific navigational platform. After confirming the patient meets the eligibility criteria, the patient will be approached for enrollment in the study. Written research informed consent for the collection of data will be integrated within the clinical workflow when obtaining procedural consent as described below.

# STATISTICAL CONSIDERATIONS

## Sample Size Calculation

EMN diagnostic yield varies widely in the literature (1). Based on data from prior studies and our own published data, we estimated the diagnostic yield of EMN to be 80% (10, 12). The diagnostic yield of SSCB has not been fully elucidated, but published data suggest an overall diagnostic yield of 80% as well (5,7). Assuming the diagnostic yield for EMN is 80%, with a non-inferiority margin set at 10%, cluster size of 2, and no intracluster correlation, we need 202 clusters (OR-days) to have an 80% power to conclude noninferiority at a one-sided type I error rate of 5%, which corresponds to a target of 425 subjects to reach 202 per arm. The noninferiority margin has been chosen based on what would be considered a clinically significant difference (or, put differently, a difference which might influence a hospital to purchase one platform over the other). In case our average cluster size does not reach 2, we will plan to increase the number of clusters to meet our target enrollment of 425 subjects to reach 202 per arm.

#### Non-Inferiority Tests for the Difference of Two Proportions in a Cluster-Randomized Design

Test Statistic: Likelihood Score Test (Farrington & Manning) Hypotheses: H0: P1 - P2  $\leq$  D0 vs. H1: P1 - P2 > D0

	Group 1	Group 2	Group 1 Group 1			Intra-			
	Clusters/	Clusters/	Group 2	Non-Inf.	Actual	Non-Inf.	Actual	Cluster	
	Items	Items	Prop	Prop	Prop	Diff	Diff	Corr.	
Power	K1/M1	K2/M2	P2	P1.0	P1.1	D0	D1	ICC	Alpha
0.80275	2/128	2/128	0.8000	0.7000	0.8000	-0.1000	0.0000	0.0000	0.025
0.80327	2/101	2/101	0.8000	0.7000	0.8000	-0.1000	0.0000	0.0000	0.050

## **Interim Analysis**

There is no plan for interim analysis and thus no boundaries for early stopping.

## **Statistical Analysis Plan**

Standard consort diagram will be created. Descriptive statistics including means, standard deviations, and median and interquartile ranges for continuous parameters, as well as percentages and frequencies for categorical parameters will be presented. To adjust for intracluster correlation, a generalized linear mixed model with binary outcome will be used to compare the primary outcome (diagnostic yield) between the comparator groups. Additional comparisons between groups will be made using either generalized linear mixed model.

Subgroup analysis will be performed for the following subgroups

- Nodule size: <1.5cm, 1.5-3cm, >3cm
- Presence of bronchus sign
- Solid vs subsolid nodule
- Peripheral vs central location Peripheral defined as outer 1/3 of chest

# **DATA COLLECTION**

All data collected is captured as part of routine clinical care and will be supplemented with abstraction from EPIC as needed. Data will be collected in a Health Insurance Portability and Accountability Act compliant REDCap database. REDCap (Research Electronic Data Capture) is a secure, web-based application that is flexible enough to be used for a variety of types of research. REDCap provides an intuitive user interface that streamlines project development and improves data entry through real-time validation rules (with automated data type and range checks).

REDCap also provides easy data manipulation (with audit trails for reporting, monitoring and querying patient records) and an automated export mechanism to common statistical packages (SPSS, SAS, Stata, R/S-Plus). In addition to traditional data capture functionality, REDCap's survey capabilities are a powerful tool for building and managing online surveys. The research team can create and design surveys in a web browser and engage potential respondents using a variety of notification methods. All data collection projects rely on a thorough, studyspecific data dictionary, defined by all members of the research team in an iterative, selfdocumenting process. This iterative development and testing process results in a well-planned and individualized data collection strategy.

REDCap servers are housed in a local data center at Vanderbilt, and all web-based information transmission is encrypted (10). REDCap was developed specifically around HIPAA-Security guidelines and is recommended to Vanderbilt researchers by both our Privacy Office and Institutional Review Board. REDCap has been disseminated for local use at more than 2,700 other academic/non-profit consortium partners in 117 countries. Vanderbilt leads the REDCap Consortium, which currently supports more than 490,000 projects and 654,000 users.

Data capture may be facilitated by the use of the REDCap Clinical Data Interoperability Services (CDIS) tools. Project team members listed as Key Study Personnel with existing electronic health record (EHR) system access rights will make use of REDCap CDIS tools. These tools are designed to enable transfer of relevant study-related data from the Vanderbilt Research Derivative and/or directly from the EHR into REDCap.

The Research Derivative is a database of clinical and related data derived from the Vanderbilt University Medical Center's (VUMC) clinical systems and restructured for research. Data is repurposed from VUMC's enterprise data warehouse, which includes data from StarPanel, VPIMS, and ORMIS (Operating Room Management Information System), EPIC, Medipac, and HEO among others. The medical record number and other person identifiers are preserved within the database. Data types include reimbursement codes, clinical notes and documentation, nursing records, medication data, laboratory data, encounter and visit data, among others. Output may include structured data points, such as ICD 9 or 10 codes and encounter dates, semi-structured data such as laboratory tests and results, or unstructured data such as physician progress reports. The database is maintained by the Office of Research Informatics under the direction of [name].

#### DATA AND SAFETY MONITORING BOARD (DSMB)

The principal role of the DSMB is to assure the safety of patients in the trial. They will regularly monitor safety data from this trial, review and assess the performance of its operations, and make recommendations to the study team and the LHS Platform with respect to:

- Participant safety and risk/benefit ratio of study procedures and interventions

- Protocol amendments (with specific attention to study population, intervention, and study procedures)

- Adherence to the protocol requirements

- Possible early termination of the trial because of new external information, early attainment of study objectives, safety concerns, or inadequate performance

The DSMB will be asked to evaluate any SAEs or unanticipated AEs. Outcomes data may be presented to the DSMB at the DSMB's request with no plan for interim analyses. The DSMB will consist of members with expertise appropriate to the conduct of the study, such as pulmonary medicine, biostatistics, and clinical trials. Appointment of all members is contingent upon the absence of any conflicts of interest. All the members of the DSMB are voting members. The Principal Investigator and unblinded study biostatistician will be responsible for the preparation of all DSMB and adverse event reports. The DSMB will develop a charter and review the protocol during its first meeting. Subsequent DSMB meetings will be scheduled in accordance with the DSMB Charter with the assistance of the Principal Investigator. The DSMB will have the ability to recommend that the trial end, be modified, or continued unchanged.

# **RISKS AND SAFETY REPORTING OF ADVERSE EVENTS**

We believe this pragmatic randomized controlled trial to be of minimal-risk given: 1) both systems are standard of care and used interchangeably for this indication; 2) both systems have comparable side effect profile, a prerequisite of the 510(k) FDA clearance of SSCB, since then backed up by additional non-randomized studies of SSCB; 3) in our current practice, it is already arbitrary whether a given patient's procedure will be performed by EMN or SSCB – all of which demonstrate equipoise between groups. Information on adverse events, whether serious or not, whether reported by the participant, directly observed, or detected by physical examination, laboratory test or other means, will be collected, recorded, followed, and reported as described in the following sections.

## **Reporting Period**

Procedural related risks are described in detail below. For example, adverse events such as pneumothorax and bronchopulmonary hemorrhage may result in the need for a chest tube or blood transfusion, respectively. These clinical adverse events are recorded within the case report form (CRF) and are known potential complications of the usual care procedures. As such, these events will not be reported to the IRB as an adverse event related to the research and instead will be collected as events for the purposes of the DSMB. All serious unanticipated adverse events will be reported to the DSMB and IRB per current institutional standards. These may include events resulting in escalation of care such as the need to remain in the hospital following the bronchoscopy procedure. As these procedures are standard of care for sampling PPLs, collection of data regarding adverse events and serious adverse events will be limited in this study:

- Any serious or non-serious adverse event related to research procedures (i.e., the consent process, HIPAA compliance, etc.) will be collected.
- Any serious adverse event that occurs  $\leq 7$  days after the procedure.
- A written report will be sent to the DSMB and IRB within 15 calendar days of the PI being notified.

## **Procedure Related Risks**

The procedures being studied are considered standard of care and are being undertaken for routine care of the patient. As such, we do not expect that enrollment in this study will result in an increased risk for the patient above what they are experiencing as part of their routine care. The risks of navigational bronchoscopy for the biopsy of PPLs are well defined, and include pneumothorax, bronchopulmonary hemorrhage, which could result in the need for a blood transfusion, respiratory failure, and anesthetic complications. Risk of death is estimated around 1/10,000. Pneumothorax is the most common complication, occurring in approximately 2% of cases in a large prospective multicenter study (3) and may result in the need for a chest tube. Existing data for SSCB indicates a similar risk profile, which also underlie its recent FDA clearance via 510(k) pathway which requires a demonstration of similar risk to a predicate approved or cleared device. Procedural risks are collected in the CRF and may be reviewed by the DSMB. As these are considered procedural risks and not research related risks, they will not be reported to the IRB.

#### **Research Only Risks**

Key additional risks for study participants are data protection and non-adherence to research consent for the collection of data. All patient related information in this study will be entered and stored at Vanderbilt University Medical Center REDCap database, which requires two factor authentications if accessed from outside of VUMC's firewall. In addition, the research paper consent will be kept in a research binder in a locked file cabinet in a locked office. Only relevant key study personnel will have access to this database and binder as necessary to conduct the research. Every effort will be made to protect the privacy of research subjects. Subject names and protected health information (PHI) will be kept confidential to the extent possible and as required by applicable laws and regulations. All records and data related to the study will be maintained in secure protected spaces, with access restricted to key study personnel approved by the IRB who (i) need access to the information to fulfill the terms and obligations under the Protocol and (ii) are under the same obligations as study personnel to keep the information confidential.

#### **REGULATORY CONSIDERATIONS**

## **Informed Consent**

We propose a pragmatic, open-label, cluster-randomized trial to compare the diagnostic yield of these standard of care bronchoscopic platforms (EMN vs. SSCB). We will randomly allocate which system (EMN or SSCB) is set-up in each operating room on a given day, and all

peripheral pulmonary lesion biopsies occurring in that room on that day will be performed with the assigned system.

We currently perform advanced diagnostic bronchoscopy in two operating rooms within the main VUMC ORs. We have one EMN system and one SSCB system. Both systems require time to set up, including moving equipment into and out the OR and running calibration steps. OR staff typically arrives one hour before procedures are scheduled to begin each day to set up. Each OR hosts 5-8 bronchoscopies daily, up to four of which on a given day may be EMN/SSCB cases (often back-to-back with each other). Additionally, these procedures need to be planned by the bronchoscopist ahead of time. To accommodate traditional individual patient-level randomization would require moving these platforms between ORs multiple times daily and planning the procedure after consent and enrollment. This would result in a tremendous disruption of our workflow, procedural delay, and suboptimal patient care rendering this study impracticable. Furthermore, about 20% of navigational bronchoscopy cases are performed only after intrathoracic lymph nodes are sampled and negative for malignancy (per rapid on-site cytological examination). Patients with evidence of cancer in their lymph nodes would no longer have an indication for navigational bronchoscopy and would then be excluded after randomization if we were to use traditional individual patient-level randomization, which would significantly impact accrual and power.

Scheduling the EMN and SSCB systems into each room in advance to allow patients to be scheduled into these rooms based on their randomized allocation appears superficially feasible but would result in procedures being delayed days to weeks potentially, as we do not always have multiple slots available for peripheral pulmonary lesion biopsy on a given day, which is not acceptable from a clinical perspective. Furthermore, we meet a large proportion of our patients the day of the procedure, thus would be unable to enroll and randomize before the day of procedure. When patients are consented for the diagnostic bronchoscopy procedure, eligible patients will then be consented for inclusion in this trial and collection of their data.

Common etiologies of peripheral pulmonary lesions include malignancy and infections, which makes nearly all of these procedures clinically urgent.

These logistical issues have two notable practical consequences:

- 1. Given the set-up time required for these bronchoscopic platforms, they cannot be moved between rooms once set up for the day.
- 2. From the perspective of an individual patient planned to undergo bronchoscopic biopsy of a peripheral pulmonary lesion, it is currently arbitrary whether their biopsy will be performed with EMN or SSCB, which depends on the day they happen to be scheduled and which of our two platforms (EMN and SSCB) happen to be set up in the OR that day. Given no comparative data exists between these two modalities, we have no clinical reason to select patients into one system versus the other. However, the provider retains autonomy to determine the most appropriate course of clinical care based on the presentation of the patient. If new information on treatment practices were to arise and one of our two platforms were recommended for specific cases, the corresponding patients would receive the appropriate treatment and would not be eligible for this study.

In the context of these issues, we believe the only feasible study design for this trial is cluster randomization as previously described. The only additional risks of participation in this study beyond SOC are confidentiality and non-adherence to research consent. All data will be maintained in a secured REDCap database by proceduralists who have already been exposed to the patient's PHI while providing clinical care. The clinical team has a REDCap database in which it is collecting data on these procedures for QI projects and QI analysis. This study will extract these data from the QI systems; no new data are being collected. Research informed consent will be obtained when clinical informed consent is obtained for the procedure. Research informed consent will be scanned, by a study coordinator, into the secured REDCap database and the research paper consent will be kept in a research binder in a locked file cabinet in a locked office. Only the study team will have access to the locked file cabinet. In addition, a note will be written in the patient's electronic medical record stating that the patient was enrolled in this study.

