## Exclusion Criteria

- 1. Enrolled in a different study requiring use of one specific platform
- 2. Subject declines to participate

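### Concealment protects which room a patient is scheduled into, but not whether the patient enters the trial: nothing requires eligibility or consent to be settled before the morning envelope is opened

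*Protocol*

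**What the plan says.** The Protocol (Randomization and Blinding) allocates the two platforms to the two operating rooms daily and states: "Allocations will be concealed in sealed envelopes which will be opened every morning by the OR staff preparing the rooms". On timing, Informed Consent adds: "OR staff typically arrives one hour before procedures are scheduled to begin each day to set up".

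The same section says "we meet a large proportion of our patients the day of the procedure" and gives this as a reason why such patients could not be enrolled ahead of time. At the procedural consent visit, "eligible patients will then be consented for inclusion in this trial and collection of their data". Recruitment and Enrollment Procedures puts confirmation of eligibility before the approach for consent. One of the two exclusion criteria is "Subject declines to participate".

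On blinding, Randomization and Blinding concedes: "It is not possible to blind the bronchoscopist or the patient to the platform used for each procedure". Only the thoracic pathologists and the schedulers are named as blinded. The scheduler places patients in rooms without knowing the allocation, and both that section and Study Procedures state the intent to enrol every eligible patient.

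Neither document says who takes research consent. Neither requires eligibility or consent to be recorded before the envelope is opened.

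**The concern.** In a cluster trial, concealment has two jobs: to keep the allocation from influencing which cluster a patient is placed in, and to keep it from influencing whether the patient becomes a participant. The sealed envelope and the blinded scheduler do the first. The second is left open if the decision to approach a patient, or the patient's decision to consent, can follow the reveal.

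The stake is the yield difference itself. If patients expected to have a low yield are less likely to enter under one platform, that arm looks better than it is. Analysis as assigned cannot restore patients who were never enrolled. In a non-inferiority trial with a 10-point margin, selective non-entry in the SSCB arm favours a false conclusion of non-inferiority; in the EMN arm it costs power.

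**Working it through.** **Sequence.**

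1. The envelope is opened at morning set-up, and staff typically arrive about an hour before the first case (Randomization and Blinding; Informed Consent).
2. A large proportion of patients are first met that day. Eligibility is confirmed, the patient is approached, and research consent accompanies procedural consent (Recruitment and Enrollment Procedures; Informed Consent).
3. A room may host up to four navigational cases a day, and the platform cannot be moved once set up (Informed Consent). For later cases it is already standing in the room.
4. About 20% of navigational cases go ahead only after lymph nodes sampled in the same session are negative (Informed Consent), so whether navigation is indicated at all can also be settled after the reveal.

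The order of envelope and consent is therefore inferred. It is most secure for same-day patients and later cases, and is not stated for each patient.

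**Inputs from the documents.** EMN yield 80%, margin 10 points, one-sided 5%, Farrington-Manning test, 202 per arm, no intracluster correlation, enrolment target 425.

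**Assumptions of this review.** 212 eligible per arm (425/2 = 212.5, rounded down); c patients left out of one arm only; 50% yield in those patients; analysed size held at 202 per arm. The test is unadjusted, whereas the SAP's primary model is covariate-adjusted.

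**Formulas.** Apparent yield in the affected arm: p* = (212p − 0.5c)/(212 − c). Probability of concluding non-inferiority: Φ{[(p1 − p2 + 0.10) − 1.645·s0]/s1}. Here p1 is SSCB and p2 is EMN, s0 is the standard error from the restricted estimates (difference fixed at −0.10), and s1 is the standard error at the actual yields.

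**The plan's own figure.** With p1 = p2 = 0.80 and n = 202, the restricted estimates are 0.7411 and 0.8411, s0 = 0.04015 and s1 = 0.03980. Then (0.10 − 1.645 × 0.04015)/0.03980 = 0.853 and Φ = 0.803, matching the 0.80327 in the Protocol's power table.

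**Worked case, 10 SSCB patients omitted, true yields 70% and 80%.** p* = (148.4 − 5)/202 = 0.7099, a shift of 0.99 points. With s0 = 0.04255 and s1 = 0.04256, (0.0099 − 0.0700)/0.04256 = −1.412 and Φ = 0.079.

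**Worked case, 10 EMN patients omitted, both true yields 80%.** p* = (169.6 − 5)/202 = 0.8149, a shift of 1.49 points. Power is 0.696.

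| Omitted (share of 212) | SSCB apparent yield, true 70% | One-sided error | EMN apparent yield, true 80% | Power |
|---|---|---|---|---|
| 0 | 70.0% | 5.0% | 80.0% | 80.3% |
| 5 (2.4%) | 70.5% | 6.3% | 80.7% | 75.4% |
| 10 (4.7%) | 71.0% | 7.9% | 81.5% | 69.6% |
| 20 (9.4%) | 72.1% | 12.5% | 83.1% | 55.0% |

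**Range.** If omitted SSCB patients would have had a 40% yield, the error is 7.0%, 9.8% and 18.4%. If their yield equals that of their arm, p* = p and the error stays at 5%.

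**The case against.** The plan has real protections. Procedures are prescheduled (SAP, Randomization) by someone without knowledge of the allocation. All eligible patients are to be approached and enrolled. Research consent covers data collection only, and navigational cases use the platform in their room, so declining the research does not by itself change the platform and gives little arm-specific reason to refuse. The SAP's primary model adjusts for lesion size, density, peripheral location and bronchus sign, which mark many hard cases. A CONSORT diagram is planned. Informed Consent also explains why patient-level randomization and advance enrolment were rejected.

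All of this stands as reducing the risk. It does not remove it. Enrolling everyone is an intent with no stated check, adjustment reaches only measured factors, and the documents do not specify a by-arm account of scheduled patients who did not enter.

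Three stronger readings are tempting and not supported:

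- A reader might infer that clinicians may drop patients they judge unsuitable once the platform is known. The exclusion criteria contain no such ground, and failing to approach an eligible patient would depart from the Protocol. The sentence preserving provider autonomy follows a statement that there is no clinical reason to prefer either platform, and the text after it ties platform-based ineligibility to new information. If the platform were changed for an enrolled patient, the as-assigned analysis would keep that patient.
- A reader might infer that unblinded clinicians always take consent after the reveal, or that selection has occurred. The consent-taker is not named, the order is not given patient by patient, and the documents show only that selection is possible.
- A reader might carry the 1.5- and 3-point shifts found in an 80% arm over to the error rate and obtain about 10% and 18%. That error applies to an SSCB arm at 70%, where the same 50%-yield omissions shift the result by 0.99 and 2.08 points and give 7.9% and 12.5%.

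**Conclusion.** The gap is real but limited. Even with exact compliance, a patient can decline with the platform known, and no record made before the reveal exists against which complete approach and enrolment could be checked. Selective non-entry of roughly 5% of one arm, at a 50% yield, would move the one-sided error from 5% to about 8% if it fell on SSCB, or power from 80% to about 70% if it fell on EMN.

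Those sizes rest on assumed numbers of omissions, all in one arm, and an assumed yield; the documents supply none of these. The direction cannot be predicted, and the effect vanishes if non-entry is unrelated to yield. This is a cheap improvement worth making, not a flaw that invalidates the design.

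**What to change.** In the Protocol's Randomization and Blinding and Study Procedures sections, add that:

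- each room's list of scheduled eligible navigational cases is fixed and time-stamped before that morning's envelope is opened;
- later removal is allowed only for refusal of consent or because navigation is not indicated, with the reason recorded;
- research consent is taken before the envelope is opened where the patient can be seen by then;
- cases added later that day are flagged.

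Under the Protocol's Statistical Analysis Plan heading, specify that the CONSORT diagram accounts for every listed patient by assigned platform: approached, declined, not started, enrolled. The "not started" category needs one definition. The Protocol and the SAP's primary outcome section date the start from induction of anesthesia, while the SAP's Analysis dataset section dates it from the start of navigation; these must be reconciled.

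The cost is one short daily step built on a schedule that already exists. Cluster randomization and the clinical workflow stay as they are. If recruitment is already advanced, the by-platform account is still useful where scheduling records permit. The remaining limit is that refusals after the reveal can be shown by arm but not prevented.
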